9.7.2.6.1 Subgroup Analysis

Subgroup analyses by timing and length of evolocumab exposure as feasible.

9.7.2.6.2 Stratified Analysis

Stratified analysis by prenatal diagnosis testing prior to versus after enrollment is planned for the primary endpoint of major structural birth defects.

9.7.2.6.3 Sensitivity Analysis for Residual Confounding and Bias

Not applicable

9.7.2.6.4 Other Sensitivity Analysis

Sensitivity analysis excluding chromosomal anomalies is planned.

9.7.2.7 External Comparisons

The overall rate/proportion of major structural **birth** defects in the Specific Evolocumab Exposed group will be compared to the most recently available rate/proportion from the MACDP, a population-based tracking system for birth defects established in 1967 in the US with careful follow-up and classification of major structural **birth** defects identified up to 1 year of age ([CDC, 2007](#)). This particular program is considered appropriate for external comparisons because it is population-based and includes a relatively high level of validation of reported defects identified in children up to 6 years of age. However, comparisons are considered secondary because there is no potential to control for differences in the MACDP methods for ascertainment of defects as well as differences in the characteristics of the source population relative to the cohort **subjects** in the Registry.

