9.3.2 Outcome Assessment

9.3.2.1 Primary Outcome

- Rate of major structural **birth** defects, where a major structural **birth** defect will be defined and classified using the CDC coding manual (CDC, 2007). This method has been previously described by the study investigators and the OTIS Research Group (Chambers et al, 2001) and has been used in previous studies conducted by this group.
 - Time Period: Major structural **birth** defects identified up to 1 year of age by the mother, the health care provider, or identified in the dysmorphological examination will be included in the primary analysis. Defects identified after 12 months to 5 years of age will be described and considered separately in the context of a possible pattern.
 - Confirmation: Independent confirmation of certain defects will be required. For example, a heart murmur thought to represent a ventricular septal defect that is ascertained by the examining dysmorphologist will be included if it is confirmed as a heart defect by cardiac ultrasound. Similarly, a midline cutaneous marker at L2-L3 noted in the dysmorphological examination will be included as occult spinal dysraphism only if confirmed by appropriate imaging studies, and in accordance with the CDC coding manual referenced above.
 - Adjudication: A co-Investigator physician with expertise in teratology, pediatrics, and dysmorphology will act as the primary adjudicator of defects classified using the CDC coding system. Verification of classifications in question are performed in 2 ways: (1) by consultation with a Medical Director for the MACDP, who has an ongoing agreement with the MotherToBaby OTIS studies to consult on classification of cases in question, and (2) through a member of the Scientific Advisory Board who has expertise in this area. At annual meetings of the Board, cases classified with major defects are reviewed and where questions arise regarding appropriate classification, primary records are reviewed by one of the members of the Advisory Board with the relevant qualifications.

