9.4.6 Dysmorphology Evaluation

All live born infants will be examined by one of a team of study-dedicated dysmorphologists, led by a co-investigator from the University of California, San Diego. All members of the team are licensed pediatricians with subspecialty fellowship training in dysmorphology and/or genetics. This team of physicians has been functioning as the specialist examiners for the current MotherToBaby/OTIS Pregnancy Studies and have completed examinations for well over **1400** infants throughout North America as part of this protocol using the same standard procedures as are incorporated in this Registry. The physical examinations evaluate infants for both major and minor structural **birth** defects which provide increased sensitivity for detecting a specific pattern of malformation should one exist. All infants will be examined as soon as is practical, and optimally within the first year of life. The Research Center will group and schedule these follow-up examinations to maximize physician blinding as to exposure status, and to minimize travel time and expense for these types of investigations.

Infant examinations will be conducted using a standard checklist of approximately 130 minor malformations included in a dysmorphology exam form (see [Appendix A, 04.E. Dysmorphology Exam Form](#)). In addition, digital photographs of the infant will be taken to aid in validating any diagnoses.

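### The external MACDP comparison uses only the all-source defect rate; a second rate without examination-only defects, and one stated MACDP age window, would partly align the two sides at little cost

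*Protocol*

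**What the plan says.** Protocol Section 9.3.2.1 defines what counts towards the primary outcome: major structural defects "identified up to 1 year of age by the mother, the health care provider, or identified in the dysmorphological examination will be included". Age at detection already sorts the cases: "Defects identified after 12 months to 5 years of age will be described and considered separately". For some findings, "Independent confirmation of certain defects will be required".

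The third detection source is arranged by the study. Section 9.4.6 states: "All live born infants will be examined by one of a team of study-dedicated dysmorphologists". It adds: "Infant examinations will be conducted using a standard checklist of approximately 130 minor malformations included in a dysmorphology exam form".

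Section 9.7.2.7 sets the overall exposed-cohort rate against the latest available MACDP rate, without restricting by who found the defect. It ranks the comparison as secondary because "there is no potential to control for differences in the MACDP methods for ascertainment of defects", and because the source populations differ. It describes MACDP as a population-based tracking system for defects found in the first year of life, and then as one that "includes a relatively high level of validation of reported defects identified in children up to 6 years of age".

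The sensitivity analyses in Section 9.7.2.6 cover prenatal testing, exposure timing and length, adjudicated outcomes and chromosomal anomalies. None is by source of detection. Section 9.7.2.6.3, on residual confounding and bias, is marked not applicable.

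**The concern.** The two sides of the external comparison appear to be measured differently. Every live-born infant in the registry is due an examination by a specialist looking for structural anomalies. The protocol presents MACDP as tracking reported defects and mentions no such examination. A defect that only the study examiner notices adds to the exposed count and has no stated counterpart in the reference rate. With no drug effect, this pushes the exposed/MACDP ratio above 1.

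The protocol treats the difference as beyond control, yet its own data allow part of it to be removed. If the sentence stands, the analysis has no reason to try, and readers of a safety report would see one external ratio with no indication of how far the examination contributed.

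The age wording is a smaller matter. A 6-year reference rate against a 1-year registry rate would push the ratio down, and the section does not say outright which window supplies the reference.

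**Working it through.** The protocol gives no reference rate, test, sample size or power for the MACDP comparison, so there is no planned figure to reproduce. The check has two parts.

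**1. Can the sources be separated?**

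- Examination findings: form 04.E (Section 9.4.6).
- Mother's report: outcome interview, form 02.F (Section 9.4.3).
- Provider's report: forms 06.H and 07.I (Section 9.4.4).
- Age at detection: already used to sort defects at 12 months (Section 9.3.2.1).

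A defect that appears on 04.E and on none of the other forms by 1 year can therefore be identified. The protocol does not state that a first-finder field is held for each defect; this is inferred from the separate forms.

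**2. How much could it matter?**

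Inputs from the protocol: 60 live births and 71 observable pregnancies in the exposed cohort (Section 9.5). Assumed inputs: an MACDP rate of 3% or 4% (4% is the protocol's baseline for its internal comparison, not an MACDP figure), a true relative risk of 1, and the examination-only share.

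*Expected exposed cases with no drug effect and no extra detection:*
60 × 0.03 = 1.8; 60 × 0.04 = 2.4; 71 × 0.03 = 2.13; 71 × 0.04 = 2.84.
One case moves the rate by 1/60 = 1.7 points or 1/71 = 1.4 points.

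*Inflation of a null ratio* when a share s of counted defects is examination-only: 1/(1 − s).

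| s (assumed) | Inflation |
|---|---|
| 10% | 1/0.90 = 1.11 |
| 20% | 1/0.80 = 1.25 |
| 30% | 1/0.70 = 1.43 |

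*Worked case.* Five defects in 71 is 7.0%, which is 2.35 times 3% or 1.76 times 4%. With one examination-only case (s = 1/5 = 20%) removed, 4/71 = 5.6%, or 1.88 and 1.41 times. With two removed (s = 40%, beyond the range above), 3/71 = 4.2%, or 1.41 and 1.06 times. The exact 95% intervals are wide: 2.3% to 15.7% for 5/71 and 1.6% to 13.8% for 4/71.

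*Chance of a false high signal.* Section 9.7.2.7 names no test. For illustration, take an exact one-sample binomial with an upper tail of at most 0.025. The critical count is 6 for a 3% reference and 7 for 4%, at n = 60 or 71. The implied share is extra/(reference + extra).

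| Extra prevalence from examination-only defects (assumed) | Implied share s | Apparent ratio | False high signal |
|---|---|---|---|
| 0 | 0 | 1.0 | 0.9% to 2.3% |
| 0.5 points | 11% to 14% | 1.12 to 1.17 | 1.8% to 4.0% |
| 1 point | 20% to 25% | 1.25 to 1.33 | 3.0% to 6.5% |
| 2 points | 33% to 40% | 1.50 to 1.67 | 6.7% to 14.4% |

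The last row lies outside the 10% to 30% range and is an outer case.

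**The case against.** The strongest reply is that the plan already discloses the limitation and acts on it. Section 9.7.2.7 names the ascertainment difference and makes the comparison secondary for that reason. The primary contrast is with Comparison Group I, whose infants have the same examination. Read literally, the sentence is about MACDP's methods, which the registry cannot change; subsetting the registry's own cases alters one side only. All of this stands, and it keeps the point small. It does not justify saying that there is no potential for control at all.

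Three stronger readings are tempting and not supported.

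- **That the examination is the largest difference, or that the comparison cannot be interpreted.** The protocol ranks no source of difference above another and does not say in words that MACDP lacks a specialist examination. It credits MACDP with careful follow-up and a relatively high level of validation.
- **That the restricted rate should replace the all-source rate as the main external figure.** Women whose first contact follows a prenatal diagnosis of a major defect are excluded (Section 9.2.3.2), and Section 9.9 accepts that enrolling after a clear prenatal test may lower the defect rate. Removing only the upward component could deepen an undercount. The examination is preferably at or after 6 months, so some defects first seen there would have surfaced in routine care before 12 months.
- **That the 1-year and 6-year statements contradict each other.** They may describe two features of one program: the window for defects followed and classified, and the span of validation. The wording needs settling, but age is largely aligned already.

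The requirement for independent confirmation of certain findings limits false positives; it does not cancel extra detection of real defects.

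**Conclusion.** The point holds in a limited form. Section 9.7.2.7 sets an all-source exposed rate, including examination-only defects, against a surveillance rate for which no equivalent examination is described, and it overstates the case in saying that ascertainment differences cannot be controlled. Partial control is possible with data already collected.

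This component of bias runs one way, upwards in the exposed/MACDP ratio. Its size is unknown. Under assumed shares of 10% to 30%, a null ratio would read 1.11 to 1.43, in a comparison resting on about 2 to 3 expected cases, where one or two cases visibly move the ratio and sampling error is large in any event. The conclusion rests on the inference that MACDP has no comparable examination, and on examination-only defects being identifiable from the separate forms. The net direction of all differences together is not known, since the prenatal-diagnosis exclusion lowers the registry rate.

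The primary analysis is untouched. This is a cheap improvement, not a flaw that threatens the study's conclusions.

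**What to change.** In Section 9.7.2.7:

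1. Keep the all-source exposed rate against MACDP. Beside it, add a sensitivity comparison that leaves out defects identified only by the study dysmorphology examination, counting defects up to 1 year of age.
2. State that the MACDP reference is the rate for defects identified up to 1 year, matching Section 9.3.2.1, and reconcile the 6-year wording with this.
3. Replace the claim of no potential for control with a statement that *only partial control is possible*. Note that source-population differences remain, as does the exclusion of prenatally diagnosed defects, which lowers the registry rate.
4. Confirm that the database can show, for each major defect, which sources reported it by 1 year.

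The cost is one extra tabulation and a few sentences. The restricted rate may miss defects that routine care would have found later in the first year, so it should be presented as a lower bound beside the all-source rate and not as a replacement.

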9.7.3 Analysis of Safety Outcomes

Apart from the primary and secondary analyses, no other Safety analyses are planned as part of this study.

9.8 Quality Control

Outside of the Quality Control measures outlined in [Section 9.3.4](#) (Validity and Reliability) and [Section 9.6](#) (Data Management), the Registry will make use of a scientific advisory board external to Amgen. The primary objective of the advisory board is to review the accumulating summary data reports from the study to evaluate the possible risks to the pregnancy, paying particular attention to the risk for major structural birth defects in infants whose moms were exposed to evolocumab. The advisory board makes recommendations regarding the conduct of the study in order to safeguard the interests of registry **subjects** while preserving the integrity and credibility of the study.

Specifically, the advisory board is responsible for evaluating the accumulated summary data and determining whether there are any safety concerns. The advisory board can recommend that the conduct of the study should be altered. Members of the advisory board are also responsible for maintaining confidentiality regarding the data that are provided to the board in interim and annual reports from OTIS and data from the Registry presented at board meetings by teleconference or face-to-face.

The advisory board is also available for ad hoc consultation, data review, and advice, and is typically composed of external experts in the field of obstetrics, dysmorphology/ genetics, epidemiology, and a physician who specializes in the condition/disease that is being treated (eg, FH). Sponsor representatives can also be included as non-voting members of the advisory board.

9.9 Limitations of the Research Methods

The primary limitation of a cohort study utilizing volunteer subjects is selection bias. The use of comparably selected comparison women will address this concern to some extent, and support internal validity of the results. The use of a volunteer sample may not be representative of the entire population of evolocumab-exposed pregnancies. However, use of a disease-matched comparison group will allow for internal validity of comparisons.

It is likely that women prescribed evolocumab will be more severely diseased than the women in Comparison Group I (disease-matched control group), leading to confounding by indication. In addition, subjects in the Evolocumab-Exposed group are more likely to be exposed to additional medications to lower their LDL-C levels (including multiple medications and higher doses). Confounding by indication may also vary over time with increased awareness and access to the drug. In order to attempt to mitigate biases associated with confounding by indication, the Registry proposes to collect careful measurements of comorbidities including maternal cholesterol levels and comorbidities including cardiovascular disease history that are likely to differ across cohorts. Additionally, methods such as propensity scores may be utilized in attempts to balance covariates between comparison groups. Nonetheless, unmeasured confounding remains a limitation of the observational study design and should be recognized when interpreting results.

It is unknown to what extent women who agree to enroll in the cohort study may represent particularly high or low risk pregnancies. However, the study results will be strictly applicable to women fitting the profile of the sample of women who enroll.

The overall sample size is expected to be modest and limits the statistical power to detect differences on the primary and secondary endpoints. However, given the necessity and value of the study questions, we will capitalize on getting the most complete data possible regardless of the expected low frequency of pregnancy exposure to evolocumab.

Another limitation of the study design relates to the evaluation of spontaneous abortion rates. Rates of early spontaneous abortion (ie, at < 6-7 weeks post-LMP) will not be measured in a study that enrolls women after recognition of pregnancy. The study results with respect to spontaneous abortion will be limited to hazards of late first-trimester and early second- trimester pregnancy loss.

Because early prenatal diagnostic testing is prevalent in the US and Canada and increasingly performed prior to the second trimester, it may be difficult to achieve adequate numbers of subjects if all pregnancies with prior prenatal testing are excluded from the analysis. Therefore, the Registry will include pregnancies in the cohort study that are enrolled prior to outcome but after a prenatal test has been performed, as long as the test does not indicate a major structural **birth** defect. The FDA guidance document acknowledges that such an approach may be necessary to accrue adequate numbers ([FDA, 2002](#)). However, this practice could potentially bias the results by lowering the overall incidence of birth defects. The data analysis will address this by stratifying on use of prenatal testing and on gestational timing of enrollment (prior to prenatal testing). In addition, women who are excluded from the cohort portion of the study due to prenatal diagnosis of a major **structural birth** defect prior to enrollment will be eligible for enrollment in the Registry General Evolocumab-Exposed case series; thus these data will be captured.

It is expected that some exposures to evolocumab will occur in unintended pregnancies and unplanned pregnancy may be risk factor for adverse outcomes, for example, because the mother does not start taking prenatal vitamins until after recognition of pregnancy. Although more than half of all pregnancies in the US are unintended ([Henshaw, 1998](#)), it is possible there could be imbalances among comparison groups. This factor will be taken into consideration in the recruitment of comparison groups using the results from the interim analysis as a guide for correcting imbalances in the future. However, differences between groups will also be addressed in the statistical analysis.

The study design has relative strengths with respect to the control of a large number of potential confounders. Information will be collected repeatedly throughout pregnancy on

a variety of factors which may be related to exposure and to pregnancy outcome, such as maternal cholesterol levels and comorbidities including cardiovascular disease history, obesity, diabetes, and hypertension. The use of a disease-matched comparison group addresses to some extent the issue of confounding by indication.

Misclassification bias due to poor recall is thought to be reduced in prospective study designs such as this. In addition, each subject is interviewed at several predetermined intervals during pregnancy. Misclassification bias regarding outcome is minimized in this study design through the use of a specialized physical examination and a standardized evaluation protocol.

Another strength of the study design is the anticipated minimal lost to follow-up rate. Based on previous experience of the investigators in the MotherToBaby/OTIS Pregnancy Studies, and the frequent subject contact, lost to follow-up is typically < 5% and therefore is not expected to pose a threat to the validity of study results. A subject meeting the criteria for enrollment is considered “lost to follow-up” if follow-up information on the outcome (live birth, fetal loss) is not obtainable, or for a live birth if the birth defect status is designated as “unknown” as of 12 months following the estimated due date. Before a **subject** is designated as lost to follow-up, the subject or reporter receives at least 3 reminder telephone calls (documented in database) followed by written correspondence; alternative contact information that is requested upon enrollment is also utilized. All follow-up attempts are documented. Losses to follow-up are tallied in the Registry Interim Reports. No imputation of missing data is planned.

Finally, the primary strength of the cohort study portion of the Registry is its sensitivity for detection of a pattern of malformation. As the known teratogens are associated with specific patterns of malformation, this study design, by virtue of providing study-related dysmorphological evaluation of prospectively ascertained and exposed infants, has the unique capability of detecting within reasonable limits such a pattern if it exists.

10. Protection of Human Subjects

This Registry will be conducted in compliance with the protocol, International Society for Pharmacoepidemiology’s Guidelines for Good Epidemiology Practices for Drug, Device, and Vaccine Research in the US, US FDA regulatory requirements, in accordance with the ethical principles of the Declaration of Helsinki (1995), and the Health Insurance Portability and Accountability Act (HIPAA) ([US Department of Health and Human Services, 2003](#); [US Department of Health and Human Services, 2002](#); [International Society for Pharmacoepidemiology, 1996](#)).

10.1 Informed Consent

10.1.1 Oral and Written Consent

The pregnant woman must agree to the oral consent form at the time of enrollment and before completing the intake interview. She must sign an informed consent in order to **complete the dysmorphology exam and the face-to-face neurodevelopmental testing**. Each **subject** will be sent 2 copies of the written informed consent document following the initial intake interview and requested to sign and return 1 copy. She must also sign for release of medical information to allow the Registry to obtain information on the pregnancy and the pregnancy outcome from the subject's obstetrician, the hospital of delivery, and any health care specialist, and for the infant from the infant's pediatrician.

The original oral and signed informed consent documents will be maintained by the Registry Office. Original copies of medical record release documents will be retained at the Registry office as well, and the copies will be sent to the institution or physician from whom records are being requested.

Pregnant women under the age of 18 who are eligible for the study and who wish to participate will require written consent of their parent or guardian prior to the initial intake interview and written assent from themselves.

Consent/assent forms and study participation will be available in English and Spanish.

